- #2. Detection rates of accessory or replaced left or right hepatic arteries, major branch of the middle hepatic vein draining the right lobe, or accessory inferior right hepatic vein(s).
- #3. Correct classification rate of major anatomic variation in portal vein branching pattern.
- #4. Measurements of the diameter and length of the hepatic arteries, portal veins and hepatic veins, including
  - a. The proper, right, middle, and left hepatic arteries.
  - b. The right portal vein at the branching point from the main portal vein.
  - c. The main portal vein diameter 1 cm distal to the bifurcation.
  - d. The right, middle, and left hepatic veins.
  - e. The major branch of the middle hepatic vein draining the right lobe at the insertion to the middle hepatic vein main stem.
  - f. The accessory inferior right hepatic vein at the insertion into the inferior vena cava.
- #5. A Likert scale which rates the examination for how badly the artifacts prevented evaluation by the reader.
- #6. The percentage of examinations with the presence of significant artifacts interfering interpretation.
- #7. The relative signal intensity of the hepatic vasculature on noncontrast and postcontrast MRA.
- #8. Acquisition time.
- #9. The percentage of examinations that caused adverse events, including contrast reactions or claustrophobia.

- *Background and Detailed Research Plan*

Potential living liver donor candidates have been evaluated for the liver and its vasculature and biliary anatomy, mostly by use of CT and CTA, which requires intravenous contrast administration and at least four phase CT scanning including CT cholangiogram. Recently, the intravenous agent for CT cholangiogram has become withdrawn from the market and unavailable. Instead, the biliary anatomy is being evaluated with MR cholangiopancreatography (MRCP). Given the ability of evaluating hepatic parenchyma and characterizing focal hepatic lesions better, MR examinations are usually performed with dynamic liver MR and MRCP protocols prior to and following the administration of intravenous gadolinium contrast. Thus, the candidates are currently being evaluated by CT, CTA, MR and MRCP, which requires high cost and at least two sessions of examinations.

If the liver and its vasculature can be well evaluated with MR and MRA, CT and CTA

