Readers will be asked to evaluate the visibility of hepatic arterial anatomic variations using a 5 point Likert scale, where 5 represents complete visibility of the anatomic variations at the level of the left and right hepatic arteries, and 1 represents a completely inadequate image (#1).

The readers will evaluate the branching pattern of the hepatic artery, portal vein and hepatic veins and categorize according to the known variations (#2 and #3).

The diameter or length of the hepatic arteries, portal veins and hepatic veins will be measured by each reader as follows:

1. The proper, right, middle, and left hepatic arteries.
2. The right portal vein at the branching point from the main portal vein.
3. The main portal vein diameter 1 cm distal to the bifurcation.
4. The right, middle, and left hepatic veins.
5. The major branch of the middle hepatic vein draining the right lobe at the insertion to the middle hepatic vein main stem.
6. The accessory inferior right hepatic vein at the insertion into the inferior vena cava.

The measurements will be done on all modalities, recorded in millimeters (#4).

Readers will be asked to rate the degree of interference in image interpretation by artifacts using a 5 point Likert scale, where 5 indicates that the image is completely unaffected by artifacts, and 1 indicates that the severe artifacts prevent readers from interpreting images and recognizing anatomical structures (#5). We will categorize these scores into two groups; presence or absence of significant limitation that affected the confidence of interpretation (#6).

The relative signal intensity of the hepatic vasculature will be calculated as follows: First, the reader will measure the hepatic vasculature and liver parenchymal signal intensity by ROI (region of interest). Then, relative signal intensity (SI) will be calculated as:  $\text{Relative Signal Intensity} = C_{\text{vessel-liver}} = (SI_{\text{vessel}} - SI_{\text{liver}}) / SI_{\text{vessel}}$  (#7).

The acquisition time of each MR sequence on the scanner monitor will be recorded in minutes (#8).

Adverse events will be evaluated by the study coordinator at the time of imaging and will be reported (#9).

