Data for this study will be entered into a REDCap database, which uses a MySQL database via a secure web interface with data checks used during data entry to ensure data quality. REDCap is a free, secure, web-based application designed to support data capture for research studies. The system was developed by a multi-institutional consortium initiated at Vanderbilt University (7).

- *Statistical analysis plan:*

**Power and Sample Size:** The study will recruit 10 study participants. The study is designed to estimate parameters for a detailed power analysis for a further, larger, confirmatory study.

With 10 participants, the half width for the 95% confidence interval for the proportion of examinations with artifacts will be no more than 0.31.

We describe the analysis plan for Hypothesis #4. The other analysis plans are exactly parallel.

We will fit a general linear multivariate model with doubly repeated measures. The three within participant factors are imaging modality, location (hepatic vein, hepatic artery, and portal vein) and reader. The four imaging modalities are Inhance 3D Velocity noncontrast MRA, Inhance Inflow IR noncontrast MRA, postcontrast MRA, and CTA. The eleven locations of measurement are: The proper, right, middle, left hepatic artery, the right portal vein at the branching point from the main portal vein, the main portal vein 1 cm distal to the bifurcation, the right, middle, left hepatic veins, the major branch of the middle hepatic vein draining the right lobe at the insertion to the middle hepatic vein main stem, the accessory hepatic vein at the insertion into the inferior vena cava. We will average across the readers. We will use an alpha-spending approach to assure an overall 0.05 level for the experiment. At the 0.04 level, we will use a Hotelling-Lawley test to assess the null hypothesis of no modality effect on any of the 11 locations of measurement. If there is a difference, we will conduct two step-down tests to assess the difference between Inhance 3D Velocity non-contrast MRA and CTA, and the difference between Inhance Inflow IR non-contrast MRA and CTA. Finally, we will assess the difference between post-contrast MRA and Inhance 3D Velocity noncontrast MRA, the difference between post-contrast MRA and Inhance Inflow IR non-contrast MRA and the difference between post-contrast MRA and CTA.

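### The diameter model uses only donors with all 44 values, but a donor may lack one or two of the vessels or a scan may fail to show them, and the plan has no rule for either case

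*Combined protocol and SAP*

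**What the plan says.** Under Hypothesis and Specific Aims, outcome #4 lists the vessels to be measured. Item f is "The accessory inferior right hepatic vein at the insertion into the inferior vena cava" and item e is the large middle hepatic vein branch from the right lobe. Outcome #2 makes the same two vessels something to be detected: "Detection rates of accessory or replaced left or right hepatic arteries, major branch of the middle hepatic vein draining the right lobe", followed by the accessory vein. The Background and Detailed Research Plan expects diameters throughout: "The measurements will be done on all modalities, recorded in millimeters (#4"). Eligibility there rests on donor criteria and on having CT and MR; neither vessel is required.

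The Statistical analysis plan states "The study will recruit 10 study participants" and "We will fit a general linear multivariate model with doubly repeated measures". It specifies the factor levels: "The four imaging modalities are Inhance 3D Velocity noncontrast MRA, Inhance Inflow IR noncontrast MRA, postcontrast MRA, and CTA", and a list opening "The eleven locations of measurement are", which includes items e and f. Five readers' values are averaged. A Hotelling-Lawley test at the 0.04 level is then to "assess the null hypothesis of no modality effect on any of the 11 locations of measurement". The same paragraph also describes location as three vessel groups (vein, artery, portal vein). The plans for the other outcomes are said to run in exact parallel.

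There is no rule for an absent vessel, for a vessel that is present but cannot be measured, for averaging when only some readers obtain a value, or for donors with incomplete data.

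**The concern.** A general linear multivariate model takes one full response vector per donor. A donor without the accessory vein has no value at that site on any modality, and so leaves the whole analysis, including the sites that were measured well.

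A vessel that is present but not seen has the same effect, and that kind of gap is not random. The research plan's lowest artifact score describes images on which structures cannot be recognised. It says noncontrast sequences have had poor quality in the past and that these two have not been tested in hepatic vessels. It also says Inflow IR was developed to suppress venous flow, while five of the 11 sites are hepatic-vein sites. Sequences tuned for veins are promised, but success is not assured. Donors who keep a full vector would therefore tend to be those whose noncontrast images were good.

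The pilot exists to supply parameter estimates for a later non-inferiority study. Modality differences and variances taken from selected, well-imaged donors can look too favourable and mis-inform the size of that study.

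**Working it through.** **1. The plan's own figure.** The only stated sample-size figure is a half-width of at most 0.31 for the 95% interval of a proportion: 1.96 × √(0.5 × 0.5 / 10) = 0.310. It reproduces, but it concerns the artifact proportion and says nothing about complete donors in the diameter model.

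**2. Inputs from the Statistical analysis plan.** There are 10 donors in one group, so error df = 10 − 1 = 9. With 4 modalities and 11 sites there are 4 × 11 = 44 reader-averaged values per donor, and (4 − 1) × 11 = 33 modality contrasts.

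**3. Room for lost donors.** The Hotelling-Lawley statistic inverts the error matrix, so error df must be at least the number of contrasts; complete donors needed = contrasts + 1.

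| Test | Contrasts | Complete donors needed | Possible with 10? |
|---|---|---|---|
| 11 sites, four modalities | 33 | 34 | No |
| 11 sites, one pair of modalities (step-down) | 11 | 12 | No |
| 9 sites (without e and f), four modalities | 3 × 9 = 27 | 28 | No |
| 3 vessel groups, four modalities | 3 × 3 = 9 | 10 | Only if none is lost |
| One site, four modalities | 3 | 4 | Yes, F(3, 7) |

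Simulated data for 10 donors gave a 33 × 33 error matrix of rank 9, which confirms the first row.

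**4. Loss from absent vessels (shares assumed).** Expected complete donors = 10 × share with both e and f.

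| Share with both | Expected complete | Chance that at least 6 of 10 are incomplete |
|---|---|---|
| 0.3 | 3 | 0.85 |
| 0.5 | 5 | 0.38 |
| 0.7 | 7 | 0.05 |

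**5. Loss from unseen vessels (visibility assumed).** Suppose every donor has both vessels, CTA and postcontrast MRA always show them, and each noncontrast technique shows each vessel independently with probability d. That is 2 vessels × 2 techniques = 4 cells, so expected complete donors = 10 × d⁴.
- d = 0.9: 10 × 0.656 = 6.6
- d = 0.8: 10 × 0.410 = 4.1

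**6. Both together.** With half the donors having both vessels and d = 0.9: 10 × 0.5 × 0.656 = 3.3 of 10.

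**The case against.** The best defence has four parts.

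- *Poor imaging is already counted.* Outcome #2 gives detection by modality for exactly these two vessels, #1 scores arterial visibility, and #5 and #6 score artifacts. This stands in part. Those outcomes sit beside the diameter analysis and do not correct it, and #2 does not cover the other nine diameter sites.
- *Only the accessory vein is plainly a variant.* Being a detection outcome does not prove that a vessel is inconstant, and the plan expects normal structures to be detected too. This is fair for site e. One such site is enough to make a donor incomplete.
- *Averaging protects the cells.* One reader's missing value among five need not empty a cell, and averaging the available sites within a vessel group could keep a donor in. The plan states neither rule, and the second could compare different vessels across modalities.
- *It is a pilot.* True, but its stated product is the set of estimates that selection would distort.

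A reader might infer more than the documents support:

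- *That several sites are variants, the middle hepatic artery among them.* That artery is listed as an ordinary site and is not in outcome #2.
- *That most donors will drop out.* This needs a complete share below about 0.5, and no prevalence is given.
- *That unseen vessels alone would leave 1.8 of 10 donors*, from 10 × 0.95³³ over all 33 MRA cells. That gives postcontrast MRA the same failure rate as the noncontrast techniques. Over the 22 noncontrast cells the result is 10 × 0.95²² = 3.2, or 6.4 at 0.98. Both versions treat cells as independent, whereas failures cluster within an examination, which raises the complete share.
- *That missing data are what defeats the joint test, or bias it towards no difference.* The 11-site test cannot be computed even with full data. The selection acts on the diameter estimates and on any reduced test.

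**Conclusion.** The concern holds in a limited form. The stated model needs 44 values per donor. At least one site, and on outcome #2's listing two, may be absent or unseen, and the plan has no rule for either. Donors may therefore be lost: 3, 5 or 7 of 10 are expected to be complete if 0.3, 0.5 or 0.7 of donors have both vessels, and fewer once visibility is allowed for. Those shares are assumptions. How many donors would really be lost cannot be settled from the documents.

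The lack of slack needs no assumption about prevalence or visibility: 33 contrasts on 9 df under the 11-site wording, and 9 on 9 under the three-group wording. The tendency of the remaining estimates to favour well-imaged donors, and so to understate modality differences, is an inference from how the data arise. Its size is unknown.

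**What to change.** In the Statistical analysis plan:

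1. Replace the joint test with a separate analysis at each site, or with a mixed model that has donor random effects and a simple covariance stated in advance. Use all available readings at the sites expected in every donor, and list those sites (on the documents' wording, the nine other than e and f). State how the 0.04 level is shared across sites, or that the results are unadjusted pilot estimates.
2. Report sites e and f descriptively, among donors in whom the vessel is present on a reference read named in advance, for example the majority CTA read of the existing five readers. List separately any vessel seen only on MRA.
3. Give absent and present-but-not-measurable separate REDCap codes before reading starts, because blanks cannot be sorted reliably afterwards. State how values are averaged when some readers record none.
4. Report the percentage not measurable by modality beside each diameter difference. State that the mixed model alone does not remove bias when missingness depends on image quality.
5. Reconcile the three-location and 11-location wording, and say which of these rules carry over to the outcomes analysed in parallel.

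The cost is SAP wording, one extra code per site, and a descriptive result only for the two detection-outcome vessels. No extra scans, donors or readers are needed.

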Readers will be asked to evaluate the visibility of hepatic arterial anatomic variations using a 5 point Likert scale, where 5 represents complete visibility of the anatomic variations at the level of the left and right hepatic arteries, and 1 represents a completely inadequate image (#1).

The readers will evaluate the branching pattern of the hepatic artery, portal vein and hepatic veins and categorize according to the known variations (#2 and #3).

The diameter or length of the hepatic arteries, portal veins and hepatic veins will be measured by each reader as follows:

1. The proper, right, middle, and left hepatic arteries.
2. The right portal vein at the branching point from the main portal vein.
3. The main portal vein diameter 1 cm distal to the bifurcation.
4. The right, middle, and left hepatic veins.
5. The major branch of the middle hepatic vein draining the right lobe at the insertion to the middle hepatic vein main stem.
6. The accessory inferior right hepatic vein at the insertion into the inferior vena cava.

The measurements will be done on all modalities, recorded in millimeters (#4).

Readers will be asked to rate the degree of interference in image interpretation by artifacts using a 5 point Likert scale, where 5 indicates that the image is completely unaffected by artifacts, and 1 indicates that the severe artifacts prevent readers from interpreting images and recognizing anatomical structures (#5). We will categorize these scores into two groups; presence or absence of significant limitation that affected the confidence of interpretation (#6).

The relative signal intensity of the hepatic vasculature will be calculated as follows: First, the reader will measure the hepatic vasculature and liver parenchymal signal intensity by ROI (region of interest). Then, relative signal intensity (SI) will be calculated as:  $\text{Relative Signal Intensity} = C_{\text{vessel-liver}} = (SI_{\text{vessel}} - SI_{\text{liver}}) / SI_{\text{vessel}}$  (#7).

The acquisition time of each MR sequence on the scanner monitor will be recorded in minutes (#8).

Adverse events will be evaluated by the study coordinator at the time of imaging and will be reported (#9).

Data for this study will be entered into a REDCap database, which uses a MySQL database via a secure web interface with data checks used during data entry to ensure data quality. REDCap is a free, secure, web-based application designed to support data capture for research studies. The system was developed by a multi-institutional consortium initiated at Vanderbilt University (7).

- *Statistical analysis plan:*

**Power and Sample Size:** The study will recruit 10 study participants. The study is designed to estimate parameters for a detailed power analysis for a further, larger, confirmatory study.

With 10 participants, the half width for the 95% confidence interval for the proportion of examinations with artifacts will be no more than 0.31.

We describe the analysis plan for Hypothesis #4. The other analysis plans are exactly parallel.

We will fit a general linear multivariate model with doubly repeated measures. The three within participant factors are imaging modality, location (hepatic vein, hepatic artery, and portal vein) and reader. The four imaging modalities are Inhance 3D Velocity noncontrast MRA, Inhance Inflow IR noncontrast MRA, postcontrast MRA, and CTA. The eleven locations of measurement are: The proper, right, middle, left hepatic artery, the right portal vein at the branching point from the main portal vein, the main portal vein 1 cm distal to the bifurcation, the right, middle, left hepatic veins, the major branch of the middle hepatic vein draining the right lobe at the insertion to the middle hepatic vein main stem, the accessory hepatic vein at the insertion into the inferior vena cava. We will average across the readers. We will use an alpha-spending approach to assure an overall 0.05 level for the experiment. At the 0.04 level, we will use a Hotelling-Lawley test to assess the null hypothesis of no modality effect on any of the 11 locations of measurement. If there is a difference, we will conduct two step-down tests to assess the difference between Inhance 3D Velocity non-contrast MRA and CTA, and the difference between Inhance Inflow IR non-contrast MRA and CTA. Finally, we will assess the difference between post-contrast MRA and Inhance 3D Velocity noncontrast MRA, the difference between post-contrast MRA and Inhance Inflow IR non-contrast MRA and the difference between post-contrast MRA and CTA.

We will examine jackknifed studentized residuals for the presence of outliers and strongly influential observations, using Cook's D to evaluate the significance of the outliers. We will conduct testing for multivariate normality. We will report p-values, parameter estimates, 95% confidence intervals, and produce graphs showing the relationship between the modalities.

We will use the parameter estimates to conduct a power and sample size analysis for a second, larger, confirmatory study, designed to show the non-inferiority of the new modalities to both post-contrast MRA, and CTA.

- *Detailed Budget and Justification:*

Two noncontrast MRA techniques for three vascular structures including hepatic artery, portal vein, and hepatic veins will add 6 sequences and 30 minute to MRI time.

\$283.10 per patient for the additional MRI time (30 minutes) x 12 (2 optimization MRA scans and 10 subjects) = \$3,397.20.

Research assistant: [name]. One 50% full time employed (FTE) research assistant who will work on the entire project during the 6 months. She is needed to help with participant appointment scheduling and do all the evaluation part of the donors and will be the one of the five readers, as she is a qualified radiologist. She will be responsible for researching as well as recording and managing the data, including measures, scores, files and health records. She will assist in ongoing literature review, document review for project, qualitative and quantitative data entry and management, data analysis and checking. She will be responsible for preparing the paper and presentation of the preliminary results for journals, meetings.

1 research assistant at 50% FTE salary for 6 months;  $\$35,200 \times 0.5 \times (6/12) = \$8,800$  for 6 months.

Total amount:  $\$3,397.20 + \$8,800 = \$12,197.20$

- *Journals to which we plan to submit the study:*

Journals in which we wish to publish the results include: Radiology, Journal of Magnetic Resonance Imaging (JMRI), American Journal of Roentgenology (AJR), Hepatology and Journal of Hepatology.

- *Meetings at which we plan to present the study:*

Academic meetings at which we wish to present the results include: The International Society for Magnetic Resonance in Medicine (ISMRM), Radiological Society of North America (RSNA), The American Roentgen Ray Society (ARRS), Society of Abdominal Radiology (SAR), and American Society of Transplant Surgeons (ASTS).

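### Hypothesis #4: the 0.04-level global test over 11 locations has 33 dimensions against 9 error degrees of freedom, so it cannot be computed with 10 participants

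*Combined protocol and SAP*

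**What the plan says.** All of this is in the combined protocol and SAP, under the statistical analysis plan.

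- Sample size: "The study will recruit 10 study participants".
- Scope: "We describe the analysis plan for Hypothesis #4", followed by "The other analysis plans are exactly parallel". The aims section lists nine outcomes, #1 to #9.
- Model: a general linear multivariate model. "The three within participant factors are imaging modality, location (hepatic vein, hepatic artery, and portal vein) and reader". The next sentences name four modalities and then list eleven measurement locations. Readers are averaged.
- Error control: "We will use an alpha-spending approach to assure an overall 0.05 level for the experiment".
- Global test: "At the 0.04 level, we will use a Hotelling-Lawley test". The stated purpose of that test is "to assess the null hypothesis of no modality effect on any of the 11 locations of measurement".
- Follow-ups: "If there is a difference, we will conduct two step-down tests", one for each noncontrast technique against CTA. Three comparisons involving postcontrast MRA come last, introduced only by a word of sequence.

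The 0.04 is the only test level given. The plan also commits to reporting p-values, estimates and 95% confidence intervals, and to using the estimates to size a later non-inferiority study.

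**The concern.** The global test for #4 is the gate to the two comparisons with CTA, which bear most directly on whether CTA could be dropped. A multivariate test of this kind inverts an error matrix, and that matrix is singular when the number of dimensions exceeds the error degrees of freedom. If so, the gate has no p-value, and the analyst must choose a substitute at analysis, possibly after seeing the data.

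A secondary concern is that a reader cannot tell which p-values the 0.05 is meant to cover. The follow-ups have no level, and the last three have no stated condition.

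**Working it through.** **Inputs.** Participants n = 10, modalities 4, locations 11 or 3, and levels 0.05 overall and 0.04 global are all from the statistical analysis plan. No between-participant factor is named, so error df = 10 − 1 = 9. Averaging over readers removes that factor and adds no degrees of freedom.

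**1. Dimension of the stated null.** Four modalities give 4 − 1 = 3 contrasts. Over 11 locations, p = 3 × 11 = 33. With one group, the Hotelling-Lawley test is Hotelling's T², and F = T² (n − p) / [(n − 1) p] on (p, n − p) df. Here n − p = 10 − 33 = −23, so no such F exists. A numerical check gives the 33 × 33 error matrix rank 9 at n = 10, 32 at n = 33, and full rank first at n = 34.

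**2. Follow-ups.** A two-modality comparison taken jointly over 11 locations has p = 11 > 9 and also fails; it would need at least 12 participants. The plan does not say whether follow-ups are joint, so this part is conditional.

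**3. The three-vessel-type reading.** p = 3 × 3 = 9 and n − p = 1, so the test is F(9,1), with critical value 376 at 0.04. One participant with a missing value makes it incomputable.

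For power, assume the modalities are independent with equal variance, the locations are independent, and one modality is shifted by 1 SD at all three types.
- Each location contributes (1 − 1/4) = 0.75 to the squared distance, so D² = 3 × 0.75 = 2.25.
- Noncentrality is 10 × 2.25 = 22.5, and power is 0.076.

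**4. Computable alternatives.**
- *One summary per modality* (mean over locations): p = 3, F(3,7), critical value 4.81 at 0.04. In the step 3 scenario the noncentrality is again 22.5 and power is 0.82. With an assumed correlation of 0.3 between locations, the variance of the mean is (1 + 2 × 0.3)/3 = 0.533, D² = 0.75/0.533 = 1.41, noncentrality is 14.1, and power is 0.61. Equal shifts in one direction favour a mean.
- *A separate F(3,7) at each of 11 locations with Holm*: the first step is at 0.04/11 = 0.0036, with critical value 12.2. A 1 SD shift at a single location has noncentrality 10 × 0.75 = 7.5 and power of about 0.06 at that step. This keeps the location-wise null at a clear cost per location.

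**5. Outcomes that are not affected.** #1 and #5 have one Likert score per examination. Averaged over readers, these give 3 contrasts on 9 error df, again F(3,7).

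**6. The 0.05 statement.**
- *If it covers all nine hypotheses:* global tests at 0.04 alone total 9 × 0.04 = 0.36 at most, or 1 − 0.96⁹ = 0.307 if independent.
- *If it covers each hypothesis:* 0.05 − 0.04 leaves 0.01, which the plan does not assign.

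Take the second case with a single-summary gate at 0.04 and all five follow-ups gated at 0.01 each. With no differences, error is at most 0.04. If any modality differs, at most three of the five pairwise nulls are true: three when only one noncontrast technique differs, fewer in the other patterns. Error is then at most 3 × 0.01 = 0.03. Simulation at n = 10 on one summary measure gives 0.040 under the complete null and 0.009 to 0.028 otherwise. With the last three comparisons ungated at 0.01 each, the complete-null error is 0.052.

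**The case against.** Several points against this are fair.

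- **Pilot status.** The study exists to estimate parameters, non-inferiority is deferred, and no decision rule uses these p-values. This stands, and it limits the consequence.
- **Another model would run.** Treating modality as a row factor blocked by participant gives 11 dimensions on 9 × 3 = 27 error df. That is computable, but it is not the model described, which makes modality, location and reader all within-participant dimensions.
- **The three-type reading is computable.** True, but barely, and it does not test the null stated for 11 locations.

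Three stronger readings are tempting and are not supported.

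- *The 0.05 promise is broken across nine hypotheses.* The sentence sits inside the worked plan for #4, so 0.05 per hypothesis is a natural reading. On that reading the promise is incomplete, not broken. With follow-ups at 0.01 or less, the simulated error is at most 0.052 even if the last three are ungated. Clear inflation (0.10 to 0.12) needs 0.04 for every follow-up, a level the plan does not give them.
- *The gate is missing altogether.* It is explicit for the two CTA comparisons. Only the three postcontrast comparisons lack a condition.
- *None of the planned tests can be computed.* The failure concerns #4. Single-score outcomes such as #1 and #5 can be tested as planned.

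**Conclusion.** The concern holds for Hypothesis #4. As written, the 0.04 global test has 33 dimensions on 9 error df and has no p-value. This follows from counting and needs no assumption about the data beyond the one-group, within-participant model that the plan describes. The plan's other description of location, as three vessel types, gives an F(9,1) test with power of about 0.08 in the scenario above; that figure rests on assumed independence and equal variances.

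The multiplicity wording is a secondary ambiguity. The figures of 0.31 and 0.36 apply only if the 0.05 is read as covering all nine hypotheses, and the text does not settle that. The overall consequence is minor to moderate, but a gate that cannot be evaluated should be replaced before analysis.

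**What to change.** Edit the SAP text; no new data are needed.

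1. **Location.** Reconcile the three-level and eleven-level definitions.
2. **Global test for #4.** Prespecify a test with clearly fewer than 9 dimensions. Two options:
   - A reader-averaged summary over locations measured on all four modalities, tested with F(3,7). Cost: effects that cancel across locations are missed, and vessels not seen on one modality drop out of the summary.
   - A separate F(3,7) at each location with Holm adjustment. This keeps the location-wise null. Cost: lower power per location.
3. **Missing vessels.** Report the number of vessels not measurable on each modality, whichever option is chosen.
4. **Scope of 0.05.** Say whether it applies to each hypothesis or to all nine. If all nine, divide it.
5. **Follow-ups.** State a level for all five, and state that the three postcontrast comparisons, like the two CTA comparisons, are made only if the global test rejects. With the single-summary test at 0.04, gated follow-ups at 0.01 each keep the error within 0.05 per hypothesis. The Holm option needs its own follow-up levels, because that bound was worked out for one summary measure.

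The cost of the 0.04 plus 0.01 rule is modest power: 0.44 to pass the gate and then detect a paired difference of 1 SD of the differences at n = 10. Splitting the remaining 0.01 as 0.002 each would lower this to 0.24.
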